6.5. Concomitant Therapy

Prestudy therapies administered up to 30 days before the first dose of study intervention must be recorded on the eCRF. Any COVID-19 vaccines administered, regardless of timing, must be recorded on the eCRF. Concomitant therapies must be recorded throughout the study, from signing of the informed consent to the last study visit.

All therapies (prescription or over-the-counter medications, including vaccines, vitamins, herbal supplements; non-pharmacologic therapies such as electrical stimulation and acupuncture) different from the study intervention must be recorded in the eCRF.

Recorded information will include a description of the type of therapy, treatment period, dosage, route of administration, and indication. Modification of an effective pre-existing therapy should not be made for the explicit purpose of entering a participant into the study.

Participants who are receiving oral 5-ASA compounds, oral corticosteroids, 6-MP, AZA, or MTX for the treatment of UC at baseline (ie, Week I-0) should maintain a stable dose for the specified period before baseline, as defined in the Inclusion Criteria (Section 5.1).

In general, participants who are receiving these medications for UC at baseline of either Induction Study 1 or Induction Study 2 (ie, Week I-0) should maintain a stable dose through Week M-44, except for oral corticosteroids. Therapies can only be discontinued or reduced in dose after Week I-0 if investigator judgment requires it because of toxicity or other medical necessity; even if the toxicity resolves, the therapy should not be restarted. Oral corticosteroids must be maintained at baseline doses during Induction Study 1 and Induction Study 2, and all participants must begin tapering oral corticosteroids at Week M-0 of the Maintenance Study, unless medically not feasible (for additional details, see Section 6.5.1).

Enrolled participants should not **initiate** any of the following concomitant UC-specific medical therapies at any time during any of the 3 studies:

- Oral or rectal 5-ASA compounds.
- Oral, parenteral, or rectal corticosteroids, including budesonide and beclomethasone dipropionate.
- 6-MP, AZA, or MTX.
- Antibiotics as a primary treatment for UC.
- Total parenteral nutrition or enteral nutrition as a treatment for UC.

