If the above medical therapies are initiated or medication doses are changed based on medical necessity as assessed by the investigator, participants should continue to attend all study visits and have all assessments. While this does not represent a deviation from the study protocol, and the participants may remain on their assigned study intervention, participants who initiate or increase the dose above baseline of these UC medications during induction (ie, Induction Study 1 or Induction Study 2) will not be eligible to enter the Maintenance Study. Treatment failures due to UC medication changes will be defined in the SAP.

Laxatives should generally be avoided and should be used only in preparation for endoscopy or other procedures.

The sponsor must be notified in advance (or as soon as possible thereafter) of any changes in concomitant therapy as noted above.

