5.3.2. Primary Estimand (Estimand 1)

The primary estimand, i.e., a precise definition of the primary targeted treatment effect is defined by the following 5 attributes:

Randomized Maintenance Treatment by Week M-44:

Experimental:

- Guselkumab 200 mg SC q4w
- Guselkumab 100 mg SC q8w

Control:

• Placebo SC

Population: Patients 18 years or older with moderately to severely active UC as reflected in the inclusion/exclusion criteria (Protocol Section 5) along with a requirement of a modified Mayo score of 5 to 9 who were induced into clinical response with guselkumab.

Variable: Clinical remission at Week M-44 (Section 5.3.1.) where participants are considered to have achieved clinical remission if they fulfill the clinical remission criteria based on modified Mayo score components (Section 5.3.1.1.), and do not experience intercurrent events in categories 1-4 and 6 (defined below) prior to the Week M-44 visit.

Intercurrent Events and Corresponding Strategies:

The following are the intercurrent events for this study:

- 1. An ostomy or colectomy (partial or total)
- 2. Have a dose adjustment (including a sham dose adjustment; Section 1.3.1)
- 3. Prohibited change in UC medication (described in Attachment 2)
- 4. Discontinuation of study intervention due to lack of efficacy or an AE of worsening of UC
- 5. Discontinuation of study intervention due to major disruption, including COVID-19 related reasons (excluding COVID-19 infection) or regional crisis in Russia and Ukraine
- 6. Discontinuation of study intervention due to reasons other than those in ICEs 4 and 5

Intercurrent events (ICEs) in categories 1-4 and 6 will be handled with the composite strategy as reflected in the variable definition. ICE category 5 will be handled by the Treatment Policy Strategy. Note that the application of ICE categories 1-3 overrides that of ICE 5. This means that a participant with ICE in categories 1-3 will be considered as not to have achieved the variable, regardless of whether the participant has had an ICE 5. For participants experiencing ICE 5, their observed clinical remission status (if available) at Week M-44 will be used.

Population-level summary:

The difference in the proportion of participants achieving the variable (as defined above for this estimand) between each guselkumab group and the placebo group.

Note: This estimand acknowledges that having an intercurrent event in categories 1-4 and 6 is an unfavorable outcome.

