- Clinical remission at Week M-44 and not receiving corticosteroids for at least 12 weeks prior to Week M-44 among the participants who were receiving concomitant corticosteroids at maintenance baseline.
- Clinical remission at Week M-44 and not receiving corticosteroids for at least 4 weeks prior to Week M-44 among the participants who were receiving concomitant corticosteroids at maintenance baseline.
- Clinical response at Week M-44 and not receiving corticosteroids for at least 8 weeks prior to Week M-44.
- Clinical response at Week M-44 and not receiving corticosteroids for at least 8 weeks prior to Week M-44 among the participants who were receiving concomitant corticosteroids at maintenance baseline.
- Change from maintenance baseline in the average daily prednisone-equivalent corticosteroid dose (excluding budesonide and beclomethasone dipropionate) at each visit through Week M-44 among the participants who were receiving concomitant corticosteroids at maintenance baseline.
- Corticosteroid-free for at least 8 weeks prior to Week M-44
- Elimination of concomitant corticosteroids for at least 8 weeks prior to Week M-44 among the participants who were receiving concomitant corticosteroids at maintenance baseline.
- Elimination of corticosteroids for at least 12 weeks prior to Week M-44 among participants who were receiving corticosteroids at maintenance baseline.
- Elimination of corticosteroids for at least 4 weeks prior to Week M-44 among participants who were receiving corticosteroids at maintenance baseline.
- Elimination of corticosteroids over time among participants who were receiving corticosteroids at maintenance baseline.
- Clinical remission, clinical response, endoscopic healing, endoscopic normalization, histologic-endoscopic mucosal healing, histologic-endoscopic mucosal healing (Alternative definition 1-2), and deep histologic-endoscopic mucosal healing at Week M-44 based on the local endoscopy subscores.

- Statistical Analysis Plan CNTO1959UCO3001 Amendment 2
- Primary and major secondary endpoints, histologic healing, histologic remission, histologicendoscopic mucosal healing (Alternative definition 1-2), and deep histologic-endoscopic mucosal healing at Week M-44 by:
 - ADT-naïve, ADT-experienced but not failed, ADT-non failure, and ADT-Failure subgroups
 - Biologic-naïve, biologic-experienced without documented failure [i.e., discontinued biologic therapy for other reasons], biologic-non failure and biologic-failure subgroups

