5.5.2. Estimands for the Other Endpoints

The attributes and strategies for the ICEs that were used for the primary estimand for the primary endpoint analysis (Section 5.3.2.) will also be used for other endpoints (Section 5.5.) except for the endpoints related to extraintestinal manifestations and UC-related hospitalization or surgery,

which will be based on data as observed. The methods to be used to analyze the other endpoints (i.e., binary, continuous, ordinal, and time to event) are defined in the Section 5.5.3. (below).

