5.5.3. Analysis Methods for the Estimands for the Other Endpoints

Unless otherwise specified, other efficacy endpoints listed and defined in Section 5.5. above will be analyzed based on **Randomized Full Analysis Set** according to randomized treatment group regardless of the treatment actually received.

All statistical testing will be performed at the 2-sided 0.05 significance level. No adjustments for multiple comparisons will be made for these other endpoints and nominal p-values will be presented.

Binary Endpoints

The intercurrent events captured for binary endpoints specified in Section 5.3.2. will be applied to each of the above binary endpoints except extraintestinal manifestations. Participants with ICEs in categories 1-4 and 6 will be considered not to have achieved the binary endpoints. For participants experiencing an ICE 5, their observed values (if available) will be used. Note that the application of ICE categories 1-3 overrides that of ICE 5.

Participants with any missing data for an endpoint after application of ICE strategies will be imputed as not achieving the associated binary endpoints. Binary endpoints will be summarized with the number and frequency of participants who achieve the endpoint by treatment group, as well as the associated 95% confidence interval. Treatment comparisons (each guselkumab group versus placebo) will be performed using CMH test stratified by clinical remission status at maintenance baseline and induction dose treatment to compare the proportion of participants achieving the endpoints. In case of rare events, the Fisher's exact test will be used for treatment comparisons.

Continuous Endpoints

The ICEs specified in Section 5.3.2. will be applied to each of the above continuous endpoints, i.e., if a participant has an ICE in categories 1-4 and 6, induction baseline values will be assigned from the point of ICE onward (i.e., no change from baseline). For participants experiencing an ICE 5, their observed values (if available) will be used. Note that the application of ICE categories 1-3 overrides that of ICE 5.

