Attachment 2 DETAILED PROHIBITED CHANGES IN UC MEDICATIONS RULES

Participants who had a prohibited change in UC medication described below are considered to have ICE 3:

- Initiation of prohibited medications or therapies as defined in the protocol (see protocol Section 6.5.2).
- Initiation of restricted medications (rectal 5-ASA compounds; parenteral or rectal corticosteroids, including budesonide and beclomethasone dipropionate).
- Increase in the dose of oral corticosteroids (excluding budesonide and beclomethasone dipropionate) > 5 mg/day (prednisone equivalent) above the maintenance baseline dose for more than 7 days after the maintenance baseline visit due to worsening of disease. This includes initiation of oral corticosteroids due to worsening of disease that lasts for more than 7 days after the maintenance baseline visit for participants who were not receiving oral corticosteroids at maintenance baseline.
- Increase in the dose of oral budesonide > 3 mg/day above the maintenance baseline dose for more than 7 days after the maintenance baseline visit due to worsening of disease. This includes initiation of oral budesonide due to worsening of disease that lasts for more than 7 days after the maintenance baseline visit for participants who were not receiving oral budesonide at maintenance baseline.
- Increase in the dose of oral beclomethasone dipropionate > 5 mg/day above the maintenance baseline dose for more than 7 days after the maintenance baseline visit due to worsening of disease. This includes initiation of oral beclomethasone dipropionate due to worsening of disease that lasts for more than 7 days after the maintenance baseline visit for participants who were not receiving oral beclomethasone dipropionate at maintenance baseline.
- Increase in the dose of oral corticosteroids (excluding budesonide and beclomethasone dipropionate) > 5 mg/day (prednisone equivalent) above the maintenance baseline dose for more than 28 days after the maintenance baseline visit due to reasons other than worsening of disease. This includes initiation of oral corticosteroids due to reasons other than worsening of disease that lasts for more than 28 days after the maintenance baseline visit for participants who were not receiving oral corticosteroids at maintenance baseline.

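### For change in corticosteroid dose, assigning the baseline value after an intercurrent event replaces recorded rescue increases, and also recorded reductions, with about zero change

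*SAP*

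**What the plan says.** SAP 5.5 lists "Change from maintenance baseline in the average daily prednisone-equivalent corticosteroid dose" at each visit through Week M-44. It excludes budesonide and beclomethasone dipropionate and covers participants on corticosteroids at maintenance baseline.

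SAP 5.5.2 carries the primary ICE strategies over to all other endpoints except "endpoints related to extraintestinal manifestations and UC-related hospitalization or surgery", which are analysed as observed. Corticosteroid dose is not exempt. For continuous endpoints SAP 5.5.3 then states: "if a participant has an ICE in categories 1-4 and 6, induction baseline values will be assigned from the point of ICE onward". It describes the result as no change from baseline.

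ICE 3 is a prohibited change in UC medication. SAP Attachment 2 includes in it: "Increase in the dose of oral corticosteroids (excluding budesonide and beclomethasone dipropionate) > 5 mg/day (prednisone equivalent) above the maintenance baseline dose". The rise must last more than 7 days if it is for worsening disease, or more than 28 days if it is for another reason.

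SAP 5.3.2 gives the intent behind the strategy: "This estimand acknowledges that having an intercurrent event in categories 1-4 and 6 is an unfavorable outcome".

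**The concern.** For Mayo scores, CRP or IBDQ the induction-baseline value represents active disease, so assigning it penalises the participant. Corticosteroid dose behaves differently. Protocol 6.5 states: "Oral corticosteroids must be maintained at baseline doses during Induction Study 1 and Induction Study 2". The induction-baseline dose is therefore normally the maintenance-baseline dose, and assigning it gives a change of about zero.

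For a participant with a qualifying rise, the event that the endpoint should register triggers its own replacement by a better value. The endpoint is meant to show whether maintenance guselkumab reduces steroid exposure compared with withdrawal to placebo. An analysis that discards recorded doses after every ICE cannot show that cleanly. The data needed are collected: concomitant therapies are recorded to the last study visit, and after a UC medication change "participants should continue to attend all study visits and have all assessments" (Protocol 6.5).

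**Working it through.** The plan gives no sample size, SD, expected effect or ICE rate for this endpoint, so there is no figure to reproduce. The check has two parts: what the rule does to single participants, and which way it moves the treatment contrast.

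**Single participants** (illustrative doses; Protocol 5.1 caps entry prednisone at 20 mg/day)

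- Rescue: 20 mg at both baselines, raised to 30 mg for worsening for more than 7 days. Recorded change +10 mg; analysed change 20 - 20 = 0.
- Completed taper, then dose adjustment: under Protocol Table 5, 20 mg falls by 5 mg/week to 10 mg (2 weeks), then by 2.5 mg/week to 0 (4 weeks). That takes 6 weeks, so 0 mg is reached at about Week M-6. Protocol 6.6.1 allows dose adjustment (ICE 2, sham included) from Week M-8. Recorded change -20 mg; analysed change 0.
- Dose reduced in induction, which Protocol 6.5 permits for toxicity or medical necessity: 20 mg at I-0 and 10 mg at M-0. The assigned induction value gives 20 - 10 = +10 mg, not the no-change result that SAP 5.5.3 describes. The endpoint is measured from maintenance baseline, but the assigned value comes from induction baseline.

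**Contrast between arms**

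Let D be the common baseline dose, with participants without an ICE tapering to 0. Let r be the share with a rescue ICE whose recorded dose is x mg above baseline. Let o be the share with another ICE after tapering by t mg. The mean change in an arm is:

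- recorded doses: -D(1 - r - o) + x·r - t·o
- SAP rule: -D(1 - r - o)
- composite score taking the larger of baseline and recorded dose: -D(1 - r - o) + x·r

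With P for placebo and G for guselkumab, the placebo-minus-guselkumab difference under the SAP rule differs from

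- the recorded-dose difference by -x(rP - rG) + t(oP - oG)
- the larger-of difference by -x(rP - rG)

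Illustration with D = 20 mg and rescue 20% on placebo vs 5% on guselkumab. All rates, x and t are assumptions.

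| Case | Other ICEs (P vs G) | t | x | Recorded | SAP rule | Larger-of |
|---|---|---|---|---|---|---|
| 1 | none | – | 10 | 4.5 | 3.0 | 4.5 |
| 2 | 30% vs 10% | 20 | 10 | 4.5 | 7.0 | 8.5 |
| 3 | 30% vs 10% | 10 | 10 | 6.5 | 7.0 | 8.5 |
| 4 | 30% vs 10% | 10 | 20 | 8.0 | 7.0 | 10.0 |

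Case 2 in full, placebo then guselkumab:

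- recorded: -20(0.5) + 10(0.2) - 20(0.3) = -14.0; -20(0.85) + 10(0.05) - 20(0.1) = -18.5; difference 4.5
- SAP rule: -10.0; -17.0; difference 7.0
- larger-of: -10.0 + 2.0 = -8.0; -17.0 + 0.5 = -16.5; difference 8.5

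Against recorded doses the SAP rule moves the contrast toward the null in cases 1 and 4 and away from it in cases 2 and 3. Against the larger-of score it moves toward the null in all four.

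**The case against.** The strongest objection is that the direction of bias is not fixed. A reader might infer from the rescue example that the rule simply dilutes the treatment effect. The documents do not support that, because the rule also cancels reductions. Dose adjustment follows loss of response, so it may well be more frequent on placebo, and cancelling reductions there widens the contrast. This stands.

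Two other stronger readings also fail:

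- That every steroid-related ICE 3 is understated by more than 5 mg/day. This is true only at visits while a qualifying prednisone-equivalent rise lasts. Visits are 4 weeks apart, so a short course can fall between them. Once the dose drops below baseline, the rule overstates steroid use in the same participant. A participant tapered to 0 and restarted at the baseline dose is not above maintenance baseline, so this criterion is not met and the recorded dose stays unless another ICE applies. Budesonide and beclomethasone increases trigger ICE 3 but lie outside this endpoint.
- That the understatement can be given as a percentage of the effect. Any such figure needs assumed rescue rates and doses, and it measures distance from whichever alternative score is chosen as reference.

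It can also be said that, with a mandated taper, no reduction is already unfavourable, and that SAP 5.3.2 does not promise the worst value. That is fair for participants whose recorded dose is at or below baseline. It does not answer the case where the recorded value is worse than the assigned one.

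Finally, steroid sparing is carried mainly by the major secondary endpoint of corticosteroid-free clinical remission and by several steroid-elimination endpoints, where an ICE 3 counts as failure. This limits the consequence but does not make the rule correct.

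**Conclusion.** The concern holds as a mismatch between rule and endpoint. For change in corticosteroid dose, the baseline assignment replaces a qualifying recorded increase with about zero change while the increase lasts, which conflicts with the SAP's stated intent. It also deletes reductions achieved before other ICEs. The zero rests on equal induction- and maintenance-baseline doses, which the protocol normally ensures but does not guarantee.

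The direction depends on the reference. Relative to a composite score that keeps recorded increases, the bias is toward the null provided rescue is more frequent on placebo. Relative to recorded doses, the sign depends on whether x(rP - rG) exceeds t(oP - oG), and the documents fix neither term. The figures in the table are illustrations, not estimates.

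The effect is confined to one endpoint with nominal p-values, in the subgroup on corticosteroids at maintenance baseline. The correction is worth making because the rule as written gives a wrong value and the right data are already collected.

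**What to change.** In SAP 5.5.2 and 5.5.3, exempt the average daily corticosteroid dose endpoint from the baseline-value assignment and analyse recorded doses as observed (treatment policy). This follows the exemption already given to UC-related hospitalization or surgery, where the outcome can likewise be an ICE. Doses no longer recorded after a participant leaves the study would fall to the planned MMRM under missing at random.

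If a composite score is kept, assign after the ICE the larger of the baseline dose and the recorded dose, and present it beside the recorded-dose analysis. It should not stand alone: in case 2 it lies further from the recorded contrast (8.5 - 4.5 = 4.0 mg) than the present rule does (7.0 - 4.5 = 2.5 mg).

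In either case, state that any baseline value assigned for this endpoint is the maintenance baseline, so that it agrees with the no-change description.

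The cost is a sentence or two in the SAP and a small programming change, with no new data.

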5.5.1. Definitions

Clinical Endpoints

- The definition for clinical remission is provided in Section 5.3.1. Definitions of clinical response, symptomatic remission, endoscopic normalization, endoscopic healing, IBDQ remission, fatigue response, histologic-endoscopic mucosal healing, corticosteroid-free clinical remission and histologic healing are provided in Section 5.4.1.1. and for modified Mayo score, partial Mayo score, full Mayo score, see Section 5.3.1.1.
- **Histologic remission:** Absence of neutrophils from the mucosa (both lamina propria and epithelium), no crypt destruction, and no erosions, ulcerations or granulation tissue according to the Geboes grading system³ (i.e., Geboes score ≤2B.0). This is equivalent to RHI-based histologic remission.
- RHI-based histologic remission: RHI ≤3 with sub-scores of 0 for lamina propria neutrophils and neutrophils in the epithelium and without ulcers or erosion according to the Robarts Histopathology Index⁹ (See Attachment 6). This is equivalent to histologic remission defined above according to the Geboes grading system (i.e., Geboes score ≤2B.0).
- NHI-based histologic remission: NHI ≤1 according to the Nancy Histological Index¹⁰ (See Attachment 5).
- **Histologic-endoscopic mucosal healing (Alternative definition 1)**: Achieving a combination of histologic remission (as defined above) and endoscopic healing (as defined in Section 5.4.1.1).
- **Histologic-endoscopic mucosal healing (Alternative definition 2):** achieving a combination of histologic remission (based on Nancy Index⁴) and endoscopic healing (as defined in Section 5.4.1.1).
- **Deep histologic-endoscopic mucosal healing:** Achieving a combination of endoscopic normalization (as defined in Section 5.4.1.1.) and histologic remission (as defined above).
- **Deep symptomatic remission**: a Mayo rectal bleeding subscore of 0 and a Mayo stool frequency subscore of 0.
- **Partial Mayo response**: a decrease from induction baseline of ≥ 2 in the partial Mayo score.

- Statistical Analysis Plan CNTO1959UCO3001 Amendment 2
- **Durable symptomatic remission:** Symptomatic remission for ≥80% of all visits between Week M-0 and Week M-44 [i.e. at least 10 of 12 visits], which must include Week M-44.
- Colonic molecular predictive signature (MPS): this is a predictive gene expression signature, initially discovered from colon biopsies collected at baseline from a subset of participants in the ACT 1 infliximab UC study⁶ refined in the PURSUIT golimumab UC study⁷ and prospectively evaluated for prediction of mucosal healing in an open-label study of 103 UC participants treated with golimumab (PROgECT)⁸ (see protocol 8.8.3 and 8.8.6).
- UCEIS: an index that provides an overall assessment of endoscopic severity of UC, based on mucosal vascular pattern, bleeding, and ulceration⁹ The score ranges from 3 to 11, with a higher score indicating more severe disease by endoscopy. The UCEIS score will be assessed only by the central video readers for all endoscopies. See Attachment 4 for more details.
- Geboes total score: the continuous histology score is derived as the sum of all Geboes Grades and may take on values from 0 to 22.
- Geboes high activity subscore: the continuous histology score is derived as the sum of Geboes Grades 3, 4, and 5 that define histologic healing and may take on values from 0 to 10.
- Geboes low activity subscore: the continuous histology score is derived as the sum of Geboes Grades 0, 1, 2A and 2B and may take on values from 0 to 12.
- Elimination of corticosteroids is defined as achieving corticosteroid-free status through Week M-44.
- **Clinical flare**: Participants who meet the following criteria will be considered to be in clinical flare:
 - an increase from maintenance baseline in the partial Mayo score (i.e., the Mayo score without the endoscopy subscore) of ≥2 points and an absolute partial Mayo score ≥4;

OR

• an absolute partial Mayo score \geq 7 points

CRP

C-reactive protein (CRP) has been demonstrated to be useful as a marker of inflammation in participants with IBD. In participants with UC, elevated CRP has been associated with severe clinical activity, an elevated sedimentation rate, and active disease as detected by colonoscopy^{10,11}. C-reactive protein will be assayed using a validated, high sensitivity CRP assay. CRP normalization is defined as CRP concentration ≤ 3 mg/L.

Fecal Calprotectin

Fecal calprotectin has been demonstrated to be a sensitive and specific marker in identifying colonic inflammation and response to treatment in participants with IBD, especially in UC^{12} .

Assays for fecal calprotectin will be performed by the central laboratory using a validated method. Fecal calprotectin normalization is defined as fecal calprotectin concentration \leq 250 mg/kg.

Patient-Reported Outcomes

IBDQ

The IBDQ¹³ is a validated, 32-item, self-reported questionnaire for participants with IBD that will be used to evaluate the disease-specific HRQoL across 4 dimensional scores: bowel symptoms (loose stools, abdominal pain), systemic functions (fatigue, altered sleep pattern), social function (work attendance, need to cancel social events), and emotional function (anger, depression, irritability). Scores range from 32 to 224, with higher scores indicating better outcomes.

The individual IBDQ dimensions will be calculated when no more than 1 item is missing in the dimension. If an item is missing, it will be estimated using the average value across the non-missing items. If any of the 4 dimensions of the IBDQ cannot be calculated, then the total IBDQ score cannot be calculated and will be missing for that visit.

- **IBDQ remission:** total IBDQ score ≥ 170 (Irvine et al, 1994¹³; Higgins et al, 2005¹⁴)
- **Maintenance of IBDQ remission:** in IBDQ remission at both Week M-28 and Week M-44 among participants with IBDQ remission at the maintenance baseline.

PROMIS-29

The Patient-Reported Outcomes Measurement Information System (PROMIS)-29 is a validated general health profile instrument that is not disease-specific. It is a collection of short forms containing 4 items for each of 7 domains (depression, anxiety, physical function, pain interference, fatigue, sleep disturbance, and ability to participate in social roles and activities). PROMIS-29 also includes an overall average pain intensity 0-10 numeric rating scale. Norm-based scores have been calculated for each domain on the PROMIS measures, with a score of 50 representing the mean or average of the reference population. On symptom-oriented domains of PROMIS-29 (anxiety, depression, fatigue, pain interference, and sleep disturbance), higher scores represent worse symptomatology. On the function-oriented domains (physical functioning and social role), higher scores represent better functioning. Additionally, the physical component summary score (PCS) and mental component summary score (MCS) will each be derived from all 7 domain scores of PROMIS-29 (Hays et al, 2018¹⁷) as measures for general health related quality (HRQOL). Higher PCS and MCS scores indicate better HRQOL.

PROMIS Fatigue 7-item Short Form

The PROMIS Fatigue 7-item Short Form (PROMIS Fatigue 7a) contains 7 items evaluating fatigue-related symptoms (i.e., tiredness, exhaustion, mental tiredness, and lack of energy) and associated impacts on daily activities (i.e., activity limitations related to work, self-care, and exercise) using a 5-point Likert scale ranging from 1 (never) to 5 (always) over the past 7 day. The raw total score (ranging from 5-35) is converted into a standardized score with a mean of 50 and a standard deviation (SD) of 10 (T-Score). Compared to the fatigue domain of PROMIS-29, PROMIS Fatigue SF 7a provides additional information to evaluate frequency of fatigue.

• **Fatigue response**: \geq 7-point improvement in PROMIS Fatigue short form 7a.

PROMIS Fatigue 5-item Short Form

PROMIS Fatigue 5-item Short Form (PROMIS Fatigue SF5a): PROMIS Fatigue SF5a is a customized short form to evaluate fatigue frequency. It consists of items 1-5 of SF7a (the name of each item is labeled as FATEXP20, FATEXP5, FATEXP18, FATIMP33, FATIMP30 from of the instrument, which are the names used in fatigue item bank from the developer). Similarly, the raw score of SF4a is the sum of score of 5 items (5-25). The raw total score is converted into a standardized T-score calibrated from the general population using a service provided by the developer.

Patient's Global Impression of Severity of Ulcerative Colitis

Participants will rate their UC disease activity at the baseline and planned visit using a 5-point scale ("None", "Mild", "Moderate", "Severe" and "Very Severe").

EQ-5D-5L

The EQ-5D-5L is a validated instrument consisting of the EuroQol 5 dimensions descriptive system (EQ-5D) and the EuroQol visual analog scale (EQ-VAS). The descriptive system comprises 5 dimensions (mobility, self-care, usual activities, pain/discomfort, anxiety/depression). Each dimension has 5 levels: no problems, slight problems, moderate problems, severe problems, and extreme problems. The respondent is asked to indicate his/her health state by checking the most appropriate statement in each of the 5 dimensions. The EQ-VAS records the respondent's self-rated health on a 20-cm vertical, visual analog scale with endpoints labeled 'the best health you can imagine' and 'the worst health you can imagine'. The respondents mark an "X" on the scale to indicate their health TODAY and then write the number marked on the scale in the box.

Health Economics

Work Productivity and Activity Impairment Questionnaire-General Health

The WPAI-GH will also be utilized to evaluate work productivity. The WPAI-GH is a validated instrument created as a patient-reported quantitative assessment of the amount of absenteeism, presenteeism, and daily activity impairment attributable to general health. The WPAI-GH consists of 6 questions to determine employment status, hours missed from work due to health problems, hours missed from work for other reasons, hours actually worked, the degree to which general health affected work productivity while at work, and the degree to which general health affected activities outside of work. Four scores are derived: percentage of absenteeism, percentage of presenteeism and presenteeism, and percentage of impairment in activities performed outside of work. Higher scores indicate greater impairment.

